Delivering Effective Non-Invasive ventilation in Motor neuron Disease

Evaluating the effectiveness of an intervention to develop intensive optimisation of non-invasive ventilation in motor neuron disease: a type 3 hybrid implementation-effectiveness, stepped-wedge cluster randomised controlled trial.

#### **Abbreviations**

#### **Definition of terms**

AE Adverse Event

CCC Confirmation of Capacity and Capability

CI Chief Investigator
CRF Case Report Form

CTRU Clinical Trials Research Unit

DMEC Data Monitoring and Ethics Committee

GCP Good Clinical Practice
ICF Informed Consent Form

ICH International Conference on Harmonisation

ISF Investigator Site File (This forms part of the TMF)

ISRCTN International Standard Randomised Controlled Trials

Number

ITT Intention to Treat

MDT Multidisciplinary Team
NIV Non-Invasive Ventilation

NHS R&D National Health Service Research & Development

ODI Oxygen Desaturation Index

PI Principal Investigator

PIC Participant Identification Centre
PIS Participant Information Sheet

QA Quality Assurance
QC Quality Control
QP Qualified Person

RCT Randomised Control Trial
REC Research Ethics Committee

SAE Serious Adverse Event
SAP Statistical Analysis Plan

SCHARR Sheffield Centre for Health And Related Research

SDV Source Data Verification

SOP Standard Operating Procedure

SSI Site Specific Information

SWAT Study Within A Trial

TMF Trial Master File

TMG Trial Management Group
TSC Trial Steering Committee

#### 1.4 Role of the Funder

The funder has reviewed the research protocol but will have no role in data collection, analysis, data interpretation, report writing or in the decision to submit the report for publication. The funder has approved the selection of members for oversight committees.

Disclaimer: The views expressed are those of the author(s) and not necessarily those of the NIHR or the Department of Health and Social Care

## 1.5 Version Control Table

Version	Version	Version	Protocol updates and finalised by;	Reasons	for
stage	number	date		update	
Draft 15 of	Draft 15 of v1.0	07Jan25	Updates to date and version	Funder	request
final			throughout.	prior to ap	proval
			Section 1.4 Addition of disclaimer.		
			Section 1.5 Replacement of table to		
			track version control.		
			Section 9.1 Addition of skin tone data		
			collection to validate oximeter data.		

# **Trial Summary**

Study title	Delivering Effective Non-Invasive ventilation in Motor neuron disease using intensive remote support (DENIM)
Sponsor	Sheffield Teaching Hospitals NHS Foundation Trust
Funder	National Institute for Health and Care Research: Health and Social Care Delivery Research (HSDR) (NIHR158715)
ISRCTN	TBC
Project start date	01/09/2024
Project end date	31/01/2028
Hypothesis, aims and objectives	Hypothesis: The addition of a highly intensive, theory-informed, goal-based NIV optimisation package during the first 12 weeks of NIV initiation will lead to increased NIV adherence (defined as the number of days in which patients use NIV for >4hr/day during week 9-12) ≥ 6 days compared to usual care NIV initiation practices in patients with motor neuron disease.  Aim: To investigate the effectiveness and cost effectiveness of implementing an intensive, theory-informed goal-based approach to NIV initiation which aims to increase NIV effectiveness in people with motor neuron disease. To determine its impact on NIV use and effectiveness and to explore contextual barriers to normalising such a service within routine clinical practice.  Objectives:  1. A stepped wedge cluster randomised controlled trial powered to detect if the addition of highly intensive, theory-

	informed goal-based approach during the first 12 weeks of NIV initiation increases NIV use and effectiveness;  2. A process evaluation showing how healthcare professionals' self-reported normalisation of this new approach to NIV optimisation within clinical teams is associated with wear time and other measures of success, with pathways to outcome further elaborated through observations, interviews and surveys;  3. An Cost-Effectiveness Evaluation Alongside a Clinical Trial and long-term cost effectiveness modelling, from an NHS perspective.
Trial design	Open label, stepped wedge cluster randomised controlled superiority trial with process evaluation and cost effectiveness evaluation
Internal pilot/feasibility criteria	Pilot green criteria:  1. Site set up  Number of centres recruited first patient: 12  (100%) at study month 14, month six of recruitment period)  2. Participant Recruitment: number of centres achieving their individual target recruitment rate (100%) at study month 20, which is month 12 of recruitment period equating to halfway through recruitment  3. Data collection: NIV adherence (primary outcome) obtained from patients who have completed the study 100% at study month 20, which is month 12 of recruitment period equating to halfway through recruitment  4. Intervention delivery: Patients received a clinical review within the specified time windows

	(week 4, intervention fidelity). 100% at study month 20, which is month 12 of recruitment period equating to halfway through recruitment
Setting	Outpatient or inpatient NIV initiation
Participants	Adults with a diagnosis of MND confirmed by a consultant neurologist and a clinical diagnosis of respiratory insufficiency according to local protocols, published guidelines and/or specialist opinion. And have respiratory insufficiency judged by the treating clinician to be severe enough to warrant long-term domiciliary NIV and requiring NIV optimisation within the duration of the study (12 weeks).
Intervention & control groups	Intervention: A theory-based package of staff education, highly intensive support, monitoring and optimisation using telemonitoring during the first 12 weeks of NIV use  Control: standard care
Primary outcome(s)	NIV usage at 12 weeks (the number of days in which patients use NIV for >4hr/day during week 9-12)
Secondary/exploratory outcome(s)	NIV effectiveness: NIV usage (w4), ventilation effectiveness (w4&12) (e.g. tidal volumes, ventilator asynchronies, apnoea hypopnoea index, leak)  Patient reported outcome measures (w12):  Quality of life (McGill quality of life questionnaire, developed for patients with a life limiting illness),  Dyspnoea-12 (measuring respiratory symptoms, sensitive to change), S3NIV (measures respiratory symptoms, sleep quality and NIV-related side effects)  Health and social care costs  EQ5D

**DENIM:** Delivering Effective Non-Invasive ventilation in Motor neuron disease using intensive remote support

	Survival follow-up minimum 12 weeks, maximum of 27 months
Duration of recruitment period and first enrolment date	1 st May 2025, 96 weeks
Duration of follow-up	12 weeks follow up. All participants survival followed up at week 108
Target sample size	252 (12 clusters)
Definition of end of trial	All participants completed 12 weeks of NIV optimisation and all participants survival collected at week 108.

## 2. Introduction

## 2.1 Background

Motor neuron disease (MND) is a terminal disease affecting 1 in 300 people. Respiratory failure is the major cause of morbidity and death. People typically die within two to four years. Non-invasive ventilation (NIV) is the only intervention that significantly improves both life expectancy and quality of life in MND[1]. It improves breathlessness, sleep disturbance and fatigue and improves survival by an average of 8 months in early trials[2] and 13 months in real-world observations[3]. Developments in respiratory care now means people with MND may live for years if successfully established on NIV [3–5]. Despite clear evidence of benefit, at least half of patients with MND are unable to gain effective NIV and do not gain the survival and quality of life benefits [5–9]. This is because effective NIV requires:

- Good adherence: NIV wear time at least four hours per day
- Effective ventilation: delivering adequate tidal volumes to reverse hypercapnoea and hypoxia, in synchrony with the patients' own breathing.

Currently guidelines for initiation of NIV in MND lack sufficient detail to achieve optimal NIV in all patients [10, 11]. NIV initiation occurs in hospitals, outpatient clinics, or homes, depending on service capabilities and patient needs. Waiting for intensive hospital initiation can delay NIV set up and reduce survival, necessitating less intensive outpatient setups. Post-initiation optimization requires periodic face-to-face visits to download NIV data and adjust ventilator settings, typically at two to four weeks and quarterly. This travel burden eventually becomes unfeasible for patients. Specialist staff are typically located in large units with limited capacity for home visits. Although guidelines recommend that staff are adequately trained and patients are effectively monitored, most home care is delivered by staff who are not MND specialists and find it difficult to support highly specialist interventions such as NIV.

#### The barriers to effective NIV

Previous research has identified the barriers and factors associated with successful NIV adherence and ventilation (Figure 1).

[figure not shown]

Figure 1 Barriers to effective NIV use and four key steps in the NIV pathway required to address these barriers.

Four key steps in the NIV pathway that are required to address these barriers (Figure 1):

#### 1. Effective preparation

Staff need to work together as a multidisciplinary team (MDT) to address all the barriers experienced by the patient and their carers to ensure they are best prepared to start NIV.

#### 2. Supported initiation

Patients can be quickly demoralised and abandon NIV if they experience problems do not perceive the benefit [12]. Starting and sustaining NIV is hard and provision of psychological and social support and training by healthcare professionals to patients and carers is vital. If patients persevere and begin to recognise symptom improvement, they can overcome these barriers[12].

## 3. Early and intensive optimisation

Adherence within the first few weeks predicts outcomes[13] and failure to achieve effective ventilation in those with established respiratory failure leads to rapid death[2] or emergency hospital admission. As patients acclimatise to NIV healthcare professionals need to rapidly identify and address problems[14].

#### 4. Ongoing monitoring

Once acclimatised patients will continue to deteriorate, and new barriers will arise which may reduce NIV effectiveness and could cause unexpected physical decline[15]. Improved

monitoring was associated with a 95% one-year adherence[15] but over three quarters of patients required longitudinal adjustments to machine settings for NIV to be optimised, impossible without monitoring.

Telemonitoring in MND provides information about NIV to healthcare professionals without needing any patient involvement. These are securely hosted cloud-based telemonitoring systems provided by the NIV companies. They provide real-time information about NIV adherence (hours used, pattern of usage), and measures of ventilation effectiveness (e.g. tidal volumes achieved, evidence of problems such as mask leakage, measures suggesting airway obstruction, ventilator asynchronies) and allow settings to be changed remotely. This can enable rapid identification and correction of the many identified barriers to NIV success. Telemonitoring improves adherence in sleep apnoea[16] and can support outpatient initiation which is a more cost-effective and faster service than inpatient initiation[17–19]. The technology is increasingly becoming available as standard on modern NIV machines but only a small number of UK MND centres are using telemonitoring in a limited way due to the time, resources and expertise required.

In addition, NIV has a substantial NHS cost (initiation alone costs est. £3575[20]) and using NIV places a high burden on patients, families and carers. Successful NIV involves a multidisciplinary approach with early preparation, supported initiation, early intensive optimisation and ongoing monitoring. This support is not yet 'normalised' into routine clinical care for MND.

## 2.2 Rationale for current study

Patients require universal good standard of NIV care that can be delivered now, to all patients, regardless of geography or NIV centre, harnessing existing and emerging technologies in a sustainable and cost-effective manner.

In order to embed and sustain the support required for effective NIV use, there must be both individual and a service level change within healthcare teams[21]. Normalization Process Theory (NPT [22]) and reference near equivalents from the Consolidated Framework for Implementation Research (CFIR[23]) and Expert Recommendations for Change (ERIC[24]) have guided the theory and structure of a 12 week intense support intervention for MND healthcare teams.

[figure not shown]

Figure 2 A programme theory articulated using Normalization Process Theory, ERIC, CIFR and empirical data from pilot work and the literature

Optimal use of NIV is not currently 'normalised' in services (implemented, embedded, spread and sustained), because there is poor *coherence*, *participation*, *action* and monitoring.

**Coherence:** professionals do not see value in optimising adherence and ventilation or differentiate our approach from the way NIV is routinely used. We address this deficit in *knowledge and beliefs* (CFIR) about NIV through *educational meetings* (ERIC, average effect size 6%[25]) and *educational materials* (ERIC, average effect size 2%[25]). Through *building coherence* (NPT mechanism) we aim to increase NIV optimisation.

**Participation:** We found a universal desire for improvement at both an individual and service level amongst professionals who deliver NIV[15]. However, these individuals (physiotherapists, nurses) do not feel confident enough or lack the resources to enact changes in their clinical practice. To address this deficit in *culture* (CFIR), we will *identify and prepare champions* (local at site and also those within the research network) (ERIC, average effect size 12%[25]) in order to increase NIV optimisation.

**Action:** Healthcare professionals told us they lack the expertise and confidence to review patients, communicate efficiently with the patient/carer and act upon the results. There is a lack of skills needed to coach patients and carers to address the whole range of biopsychosocial barriers and difficulties aligning their approach and long term need to achieve effective NIV to deliver surgical and quality of life benefit with the goals and needs of the individual and the immediate burdens of NIV[21]. Funding constraints (time, equipment) presents a major constraint to the integration of optimised NIV into clinical practice[21]. To address this deficit in self-efficacy (CFIR) we will *conduct ongoing training* (ERIC, average effect size 6%[25]) and *promote adaptability* (ERIC), through empirically observed,

context-specific strategies, such as adjusting monitoring frequency[26]. Through increasing effective collective action, we aim to increase NIV optimisation.

**Monitoring**: Staff are currently unable to tell if patients are experiencing a problem with NIV. We will address these deficits in *goals and feedback | reflecting and evaluating* using real-time telemonitoring of NIV adherence and ventilation effectiveness. Such *audit and feedback* (ERIC) confers an average effect size 4% in implementation science meta-analyses[25].

In line with the new MRC Framework[27], we have refined a programme theory stating:

#### If we:

 activate local clinical leaders/champions, provide educational materials, meetings, outreach/ongoing training and local adaptation

## We can help healthcare professionals caring for MND patients to:

- make sense of, and construct value for the timely optimisation of NIV use and ventilation, as an
  evidence-based practice, in line with NHS, professional local policies;
- get involved in ensuring patients are achieving optimal NIV
- take action, integrating NIV optimisation support into existing workload, maintaining good relationships with patients
- appraise the effectiveness of the NIV optimisation, reconfiguring it to local circumstances.

#### Then clinical teams will:

• normalise the practice of NIV optimisation

#### So that NIV is optimised:

 the average number of days patients use >4hr/day NIV will increase across the population (trial primary outcome) and patients will experience more effective NIV

## So that outcomes are improved:

- Survival and quality of life will improve across the population
- Scarce resources will be used more efficiently.

Given this theory, can we successfully change clinicians' attitudes and behaviours in order that they can change practice, so they act to intensively optimise NIV? Does this change bring out improvement in NIV effectiveness and clinical outcomes in a cost-effective manner? How can the change in practice be embedded and sustained in clinical practice in MND care centres in the UK?

The study will be conducted in accordance with the protocol and ICH GCP.

# 3. Aims and objectives

## 3.1 Hypothesis

The addition of a highly intensive, theory-informed, goal-based NIV optimisation package during the first 12 weeks of NIV initiation will lead to increased NIV adherence (defined as the number of days in which patients use NIV for >4hr/day during week 9-12) compared to usual care NIV initiation practices in patients with motor neuron disease.

#### **3.2 Aims**

The primary aim of this study is to evaluate the effectiveness of the DENIM implementation strategy, which is intended to deliver a new intensive NIV initiation service, for patients with motor neuron disease. The secondary aim is to assess the impact of the DENIM strategy on clinical outcomes for these patients, including use and effectiveness. DENIM also aims to understand the cost effectiveness of the new service and explore contextual barriers to normalising such a service within routine clinical practice.

## 3.3 Objectives

- 1. To conduct a stepped wedge cluster randomised controlled trial to detect if the addition of highly intensive, theory-informed goal-based approach during the first 12 weeks of NIV initiation increases NIV use and effectiveness:
- 2. To conduct a process evaluation showing how healthcare professionals' self-reported normalisation of this new approach to NIV optimisation within clinical teams is associated with wear time and other measures of success, with pathways to outcome further elaborated through observations, interviews and surveys;
- 3. To conduct a Cost-Effectiveness evaluation alongside a clinical trial and long-term cost effectiveness modelling, from an NHS perspective.

# 4. Trial Design

DENIM is a multicentre, type 3 hybrid implementation-effectiveness, open-label, 1:1 stepped wedged, cluster-randomised controlled superiority trial of intensive monitoring and optimisation of non-invasive ventilation verses usual care. DENIM will recruit n=252 participants.

12 UK NHS sites will open recruitment for a roll-in period of six months. As sites are opening all patients will be recruited to receive the usual care delivered at that site. Following this, every three months thereafter, two sites each will receive training and all participants at that site will receive the

intervention until all sites have begun using the intervention (recruitment 24 months + final 3 months to allow follow-up, see flow diagram, figure 3). The maximum follow-period will be 27 months (108 weeks). The total duration of the trial is 41 months.

[figure not shown]

Figure 3. DENIM Trial flow diagram

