## 7. Randomisation and enrolment

Randomisation will occur at the site (NHS Trust) level, with sites randomised to either implement the DENIM strategy or continue with usual care for NIV delivery.

This is a cluster-stepped wedge trial. UK NHS sites will open recruitment for a roll-in period of six months. As sites are opening patients will be recruited to receive the usual care delivered at that site. Following this, every 3 months thereafter, two sites each will receive training and all new patients at that site will receive the intervention until all sites have begun using the intervention.

Sites will be allocated to start the intervention in a random order using constrained random allocation, an analogue of minimisation for trials randomised at the cluster level[32]. Stratification factors will be centre size, telemonitoring use (% of patients currently used) and location of initiation (% of patients initiated as inpatient).

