## 8.1 Primary outcome/endpoint

NIV usage at 12 weeks (the number of days in which patients use NIV for >4hr/day during week 9-12).

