#### **12.1.2 Methods**

A multiple-case design will be used to capture the variation in intervention delivery across sites, explore participant responses to the trial, and barriers and facilitators to implementing the intervention. This will be conducted in all 12 sites. This will document the conditions that are necessary for goal-based approach to NIV to be normalised and obtain the perspective of professionals directly involved in intervention implementation, supporting trial recruitment and supporting participants and their families.

During the control arm phase, all sites will complete the NOMAD questionnaire[42]. Site assessment forms may also be used to provide local context prior to the intervention. Recruitment to the process evaluation interviews and observations will begin once a site switches on to the intervention. Data collection will not occur in the first 4 weeks of a site using the intervention. The NOMAD questionnaire will be completed again six months after switching to the intervention arm. We will supplement data collection with study management logs such as site assessment forms. To inform the fidelity assessment we will audit 10% of worksheets for completeness.

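### Sections 4 and 7 of the protocol disagree on whether patients already enrolled under usual care receive the intervention when their site switches, so the analysed condition is undefined for about a quarter of planned controls

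*Protocol*

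**What the plan says.** Two sections of the protocol describe the same step.

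- Section 4 (Trial Design): every three months after the roll-in, "two sites each will receive training and all participants at that site will receive the" intervention.
- Section 7 (Randomisation and enrolment): "two sites each will receive training and all new patients at that site will receive the intervention until all sites have begun" using the intervention.

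The primary outcome in section 8.1 is "the number of days in which patients use NIV for >4hr/day during week 9-12". It is therefore read two to three months after a patient starts NIV, while steps are three months apart. Section 11.2.1 assigns participants in the ITT and modified ITT sets to the intervention they were supposed to receive. The per-protocol set requires treatment in line with the protocol. Section 11.2.2 fits one intervention term, with step as a fixed effect and site as a random effect. The protocol text mentions no transition period; Figure 3 is not available in the text reviewed.

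**The concern.** For a patient recruited under usual care who is still within 12 weeks of starting NIV on switch day, section 4 read literally brings them into the intervention and section 7 leaves them in usual care. Sites could act on either. The analysis rule in section 11.2.1 cannot resolve it, because it refers back to what the patient should have received.

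If such patients receive the intervention and are still coded as controls, some of the control data carry part of the treatment effect. They fall in the site-period just before each switch, which carries heavy weight in a stepped-wedge estimate, so the dilution is larger than their share of the sample suggests. If sites follow different readings, the exposure cannot be put right afterwards.

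**Working it through.** **Inputs from the protocol**

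- Roll-in (section 4): "12 UK NHS sites will open recruitment for a roll-in period of six months".
- Length (section 4): "recruitment 24 months + final 3 months to allow follow-up". The same section equates 27 months with 108 weeks, so 3 months = 12 weeks.
- Steps (section 7): "every 3 months thereafter, two sites each will receive training". Twelve sites in pairs make six steps, taken here as recruitment months 6, 9, 12, 15, 18 and 21. This agrees with section 8.4, which has four sites switched by month 12.
- Accrual (section 11.1): 3 patients per site in the roll-in, then 1 per month in months 7-24.
- Design values (section 11.1): difference 6 days, ICC 0.05, two-sided 5%, 15% drop-out, 214 evaluable, stated power 90%. The SD is printed as ten0 and is read here as 10 (assumption).

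**The plan's own totals**

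12 × (3 + 18 × 1) = 252, and 252 × 0.85 = 214.2. Both reproduce.

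**Number of controls**

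Controls per site by switch month are 3, 6, 9, 12, 15 and 18, which sum to 63. With two sites per step, 2 × 63 = 126, half of 252.

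**Controls whose outcome window runs past the switch**

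The window ends at week 12, so it ends after the switch for anyone initiated less than 12 weeks before it. It starts after week 8, so it lies wholly after the switch for anyone initiated less than 8 weeks before it. Recruitment is taken as even: 1 per month per site, or 0.5 per month for the first pair, whose pre-switch months are in the roll-in.

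| Window | 4-week months | Calendar months |
|---|---|---|
| Ends after switch | 10 × 3 + 2 × 1.5 = 33; 33/126 = 26.2% | 10 × 2.76 + 2 × 1.38 = 30.4; 24.1% |
| Wholly after switch | 10 × 2 + 2 × 1 = 22; 22/126 = 17.5% | 10 × 1.84 + 2 × 0.92 = 20.2; 16.1% |

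With switches at months 9 to 24 instead, the shares would be 20-22% and 14-15%, but the last pair would then recruit no intervention patients.

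**Effect on the estimate if these patients are treated but coded as controls**

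The model is a standard stepped-wedge linear mixed model: 7 periods, 2 sites per step, 3 × 0.85 = 2.55 evaluable patients per site-period, fixed period effects and a random site effect, SD 10, ICC 0.05. It gives SE = 2.007 days. Power without dilution is Φ(6/2.007 − 1.96) = 84.8%. This is not the stated 90%, which came from a modified macro that is not shown; the same model gives 89.4% if all 252 are analysed.

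Let f be the share of the six-day effect gained by affected controls. In the site-period before each switch the true mean is raised by 6f (half of that for the first pair, where only half the roll-in patients are affected). The expected estimate is then 6 − 3.133f.

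| f | Expected estimate (days) | Power |
|---|---|---|
| 0 | 6.0 | 85% |
| 0.25 | 5.2 | 74% |
| 0.50 | 4.4 | 60% |
| 1 (upper bound) | 2.9 | 30% |

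The protocol gives no value for f.

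**Leaving the affected controls out**

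214.2 − 33 × 0.85 = 186 evaluable. SE rises to 2.424 and power is Φ(6/2.424 − 1.96) = about 70%.

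**The case against.** The strongest reply is that section 4 is loosely worded and section 7, which governs enrolment, states the intended rule. Several places fit that reading. The hypothesis concerns the first 12 weeks from NIV initiation. Section 6.2.2 begins with a structured assessment at initiation and a first contact at day 2. Section 6.1 speaks of people recruited to standard care, so condition seems to attach at recruitment. Section 9 sends ventilator data to the clinical team only in the intervention arm, which limits spill-over to controls. All of this stands and makes dilution less likely, but none of it rules out joining part-way, and no section settles the conflict.

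The size can also be contested, and part of that stands. Of the eight scheduled contacts, six fall by week 4. For a patient whose initiation is spread evenly over the 12 weeks before the switch, the expected number still to come is (0.29 + 0.71 + 1.43 + 2 + 3 + 4 + 8 + 12)/12 = 2.6 of 8, or 33%. If benefit tracked contacts (an assumption), the estimate would be about 6 − 3.133 × 0.33 = 5.0 days. Full gain is therefore an upper bound, not an expected case.

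A reader might infer that a quarter of controls have their whole outcome window after the switch. The accrual does not support that: the figure is about one in six, and a quarter applies only to windows at least partly after it. A reader might also take the rule in section 12.1.2, "Data collection will not occur in the first 4 weeks of a site using the intervention", as a transition period for the trial. It concerns process-evaluation interviews and observations, so it neither protects the primary outcome nor gives grounds for excluding early intervention patients.

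Finally, exposure coding and sensitivity models can be left to the SAP. That is fair for the detail, but the rule on who receives what at the switch belongs in the protocol, and the SAP cannot define the condition until the rule is fixed.

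**Conclusion.** The concern holds as a contradiction between sections 4 and 7 that leaves the analysed condition undefined for 30 to 33 of 126 planned controls (24-26%), about one in six controls (16-17.5%) having an outcome window wholly after the switch. The count rests on the stated accrual, even recruitment within each phase, switches at months 6 to 21 and no loss before week 12.

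The protocol does not show that the estimate will be biased, though a reader might infer it. Dilution arises if already-enrolled patients receive the intervention and are coded as controls, or if newly trained staff change the care of controls. With only new patients treated and no spill-over, there is none. Where it does arise, gains of 25% to 50% of the effect bring the expected estimate to about 5.2 to 4.4 days and power to about 74% to 60%. Those figures depend on the assumed gain, an SD read as 10 and a standard model whose baseline power is 85% rather than the stated 90%.

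**What to change.** 1. Reconcile sections 4 and 7 into one rule for patients enrolled under usual care and still within 12 weeks of NIV initiation at the switch. Which rule is for the trial team to decide.
2. Define each participant's analysed condition to match that rule. If already-enrolled patients remain in usual care, date of NIV initiation relative to the site's switch date is enough. If they are to receive the intervention, that coding would label treated patients as controls, and a different definition is needed.
3. Pre-specify a sensitivity analysis in which participants initiated in the 12 weeks before their site's switch form a separate exposure category, counted as neither control nor intervention.

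The cost is a protocol wording change and one extra model. Design and sample size are unchanged. Precision is lower in the sensitivity analysis only: power is about 70% if the affected controls are left out, and a separate category costs about the same.
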